#### **Functional Assessment of Chronic Illness Therapy-Fatigue (FACIT-Fatigue)**

The FACIT Measurement System is a collection of QOL questionnaires targeted to the management of chronic illness. Here, the FACIT-Fatigue will be considered.

The FACIT-Fatigue Scale is based on thirteen 5-level items (0="Not at all" to 4 = "Very much") measuring the level of fatigue over the past 7 days. Its 13-item-version assesses peripheral, central, or mixed fatigue and yields a summed total score ranging between 0 and 52. FACIT-Fatigue will be normed to 0-100. Higher FACIT-Fatigue scores indicate a lesser degree of fatigue. Notice that item 7 (I have energy) and item 8 (I am able to do my usual activities) are reversed scored. If a respondent answers at least 50% of the items of the FACIT-Fatigue questionnaire, the total score will be imputed with the average score of the answered items in the same scale as long as more than 50% ( $\geq 7$  out of 13) of the items in the scale are answered.

A summary table will show descriptive statistics (n, mean, median, SD, minimum and maximum) for the total scores and for the subscales for baseline and the post-baseline time points, as well as changes from baseline, by cirrhosis status and treatment regimen. In addition, analysis of covariance (ANCOVA) will be applied to investigate the effect of the different ABBVIE REGIMENS ( $\pm$  RBV) by cirrhosis status on FACIT-Fatigue endpoints using the corresponding FACIT-Fatigue baseline values as covariates.

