**Confidential Information**

## Annex 1. FACIT-F - The Functional Assessment of Chronic Illness Therapy-Fatigue Scale

Below is a list of statements that other people with your illness have said are important. Please circle or mark one number per line to indicate your response as it applies to the past 7 days.

		Not at all	A little bit	Some-what	Quite a bit	Very much
HI7	I feel fatigued.....	0	1	2	3	4
HI12	I feel weak all over.....	0	1	2	3	4
An1	I feel listless ("washed out").....	0	1	2	3	4
An2	I feel tired.....	0	1	2	3	4
An3	I have trouble starting things because I am tired.....	0	1	2	3	4
An4	I have trouble finishing things because I am tired.....	0	1	2	3	4
An5	I have energy.....	0	1	2	3	4
An7	I am able to do my usual activities.....	0	1	2	3	4
An8	I need to sleep during the day.....	0	1	2	3	4
An12	I am too tired to eat.....	0	1	2	3	4
An14	I need help doing my usual activities.....	0	1	2	3	4
An15	I am frustrated by being too tired to do the things I want to do.....	0	1	2	3	4
An16	I have to limit my social activity because I am tired.....	0	1	2	3	4

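### The FACIT-Fatigue scoring rule in the SAP gives a score that rises with fatigue, while the same paragraph reads a higher score as less fatigue

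*SAP*

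**What the plan says.** The FACIT-Fatigue part of SAP Section 4.2.7.2.3 makes these statements in one paragraph:

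- There are 13 items, each answered on five levels from 0 (not at all) to 4 (very much).
- On the range, the scale "yields a summed total score ranging between 0 and 52".
- On rescaling, the text is "FACIT-Fatigue will be normed to 0-100", and no formula is given.
- On reversal, the only instruction is "Notice that item 7 (I have energy) and item 8 (I am able to do my usual activities) are reversed scored", and no other item is named.
- On how the total is to be read, the stated direction is "Higher FACIT-Fatigue scores indicate a lesser degree of fatigue".

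The score is then summarised at each time point and as change from baseline. ANCOVA is used to compare the regimens within cirrhosis groups, with the comparison made "on FACIT-Fatigue endpoints using the corresponding FACIT-Fatigue baseline values as covariates".

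Protocol Annex 1 prints the questionnaire. Items 1–6 and 9–13 are statements of fatigue or impairment, beginning with "I feel fatigued". The 7th item (An5, having energy) and the 8th (An7, "I am able to do my usual activities") are the only positive statements.

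**The concern.** A summed scale needs all its items to point the same way. For a total in which higher means less fatigue, an item on which a high answer means more fatigue has to be flipped, and an item on which a high answer means less fatigue has to be left alone. Here eleven items are of the first kind and two of the second. The SAP flips the two and leaves the eleven. That also gives a coherent scale, but one that runs opposite to the direction the SAP states.

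Documenting the effect of treatment on patient-reported outcomes is a secondary objective (protocol Section 8.2.2, SAP Section 2), and FACIT-Fatigue is a named secondary variable. If the rule is programmed as written, a patient who regains energy has a falling score, and the SAP's own key reads that fall as worsening. The same sign error would carry into the regimen ANCOVA. It would also reach the interim outputs built on this score, namely the correlation with PRISM and the interaction of ribavirin with opiate substitution (SAP Section 4.2.9 and Table 13).

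**Working it through.** **Inputs.** Response coding, score range, reversal note and stated direction come from SAP Section 4.2.7.2.3. Item order and wording come from protocol Annex 1. Write x_i for the answer to item i, from 0 to 4.

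**Formulas.**

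- SAP as written: S = sum of x_i over items 1–6 and 9–13, plus sum of (4 − x_i) over items 7 and 8.
- Scoring that matches the stated direction: F = sum of (4 − x_i) over items 1–6 and 9–13, plus sum of x_i over items 7 and 8.

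**The plan's own figure.** The maximum is 13 × 4 = 52 and the minimum is 0, so the stated range of 0 to 52 is reproduced. Both S and F have this range.

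**Test patterns.**

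| Pattern (eleven fatigue items / items 7 and 8) | S, SAP as written | F, matching stated direction | No reversal |
|---|---|---|---|
| Most fatigued (4 / 0) | 11×4 + 2×4 = 52 | 11×0 + 2×0 = 0 | 44 + 0 = 44 |
| Least fatigued (0 / 4) | 11×0 + 2×0 = 0 | 11×4 + 2×4 = 52 | 0 + 8 = 8 |
| Fatigued at baseline (3 / 1) | 33 + 6 = 39 | 11 + 2 = 13 | 33 + 2 = 35 |
| Improved at follow-up (1 / 3) | 11 + 2 = 13 | 33 + 6 = 39 | 11 + 6 = 17 |

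The patient in the last two rows clearly improves. The SAP rule gives a change of 13 − 39 = −26, which the SAP's key reads as worsening. The matching rule gives 39 − 13 = +26. Reversing nothing does not help: the score still rises with fatigue, and it no longer spans 0 to 52.

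**General relation.** Each item contributes s_i to S and 4 − s_i to F, so F = 13 × 4 − S = 52 − S for every complete questionnaire. With missing items, the SAP fills in from the mean of the answered items. The prorated totals are 13 × mean(s_i) and 13 × mean(4 − s_i) = 52 − 13 × mean(s_i), so the relation still holds.

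**After norming.** The formula is not given. Assuming 100 × score / 52, the normed score is 100 minus the intended one. The example patient goes from 75 to 25 instead of from 25 to 75, and a true gain of 10 normed points appears as a loss of 10.

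**Effect on the analyses.** Both baseline and follow-up are mirrored. If F at follow-up = a + b × (F at baseline) + c × (regimen), substituting F = 52 − S gives S at follow-up = (52 − a − 52b) + b × (S at baseline) − c × (regimen). The baseline slope stays b and the regimen contrast becomes −c. Standard deviations, standard errors and p-values do not change. A correlation of the score with another variable changes sign only.

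**Search for a rule that resolves it.** Protocol Sections 9.4.1.6 and 9.7.5 describe the instrument but give no scoring algorithm. The SAP cites a scoring manual for WPAI and leaves PAM-13 scoring to an outside party. It cites no FACIT scoring manual, and none is in its reference list.

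**The case against.** The strongest reply is that calling two items reverse scored may loosely mean that they are keyed opposite to the other eleven. Read together with the direction sentence, this would lead an analyst who knows the scale to reverse the other eleven and score correctly. That reading is possible, so the documents establish a contradiction in the specification and not a wrong result already obtained. But the SAP does not say this. The ordinary meaning of its sentence is that items 7 and 8 are flipped, and no other item-level instruction exists.

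A second reply is that the paragraph could equally be repaired by keeping the reversal note and changing the direction sentence to say that higher means more fatigue. That would be coherent too. Keeping the stated direction is preferable because it leaves the SAP's interpretation of the score unchanged.

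A third is that the norming step could turn the scale round. No such step is described, and it could not help the un-normed score used in the first four interim analyses (SAP Sections 4.2.9.1 to 4.2.9.4).

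Some points on importance stand. FACIT-Fatigue is one of several secondary instruments in a descriptive study. The error loses no information and can be undone from the item data. The PRISM correlation appears only among the interim outputs. SAP Section 5 provides for program validation and plausibility checks, which might catch a reversed sign. However, validation against a faulty specification is weak protection, and the range, the spread and the p-values would all look normal.

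**Conclusion.** The concern holds. The reversal note and the stated direction cannot both be true for the questionnaire in Annex 1. Scored as written, FACIT-Fatigue is the exact mirror of what the SAP says it measures: 52 minus the intended score, or 100 minus it after norming. Every change and every regimen contrast has the right size and the wrong sign for its stated meaning.

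The contradiction follows from the documents alone. Two consequences rest on assumptions: that the rule is programmed as written, and, for the normed figures, that norming is 100 × score / 52. SVR12, the safety analyses and the study size are not affected. Because it could turn the conclusion on a secondary objective upside down without tripping a routine check, it should be corrected before the final analysis.

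**What to change.** Replace the reversal note in SAP Section 4.2.7.2.3 with an item-level rule, for example:

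> Items 1–6 and 9–13 are scored as 4 minus the response. Item 7 (An5) and item 8 (An7) are scored as answered. Reversal is applied before prorating and norming. Normed score = 100 × total / 52. A higher score means less fatigue.

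The norming formula here is the assumed one; the sponsor should confirm it. Then:

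1. Run the most and least fatigued patterns through the scoring program and confirm that they give 0 and 52.
2. Check the direction of the FACIT-Fatigue results in the interim outputs already produced, normed and un-normed, including the PRISM correlation and the ribavirin by opiate substitution interaction. Reissue any that are mirrored.

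The cost is a short SAP text change, one program check and, if needed, a rerun of the affected tables. No new data are needed and patient management is not touched.

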#### 4.2.3 Handling of missing data

No data will be imputed for any effectiveness or safety analyses except for the analyses of the HCV RNA endpoints and certain PRO endpoints. The discussion of missing data imputation for the PRO endpoints is included in section 4.2.7.2.3.

HCV RNA values will be selected for an RVR, EOTR and SVR analysis based on visit windows as defined in Table 4. When there is no HCV RNA value in a visit window based on defined visit windows, the closest values before and after the window, regardless of the value chosen for the subsequent and preceding window, will be used for the flanking imputation described below. For analysis of RVR, EOT and SVR, if a subject has a missing HCV RNA value at a post-Day 1 visit but with undetectable or unquantifiable (LLoD or LLoQ  $\leq$ 50 IU/mL) HCV RNA levels at both the preceding value and succeeding value, the HCV RNA level will be considered undetectable or unquantifiable, respectively, at this visit for this subject. In addition, if a subject has an

unquantifiable HCV RNA level at the preceding value and an undetectable HCV RNA level at the succeeding value, or vice versa, the HCV RNA level will be imputed as unquantifiable at this visit for this subject.

For analyses of RVR, subjects still missing a value for the visit after flanking imputation will be considered as a failure. For EoTR and SVR analysis, if there is no value in the appropriate window after flanking imputation but there is an HCV RNA value after the window, then it will be imputed into the EoTR or SVR window respectively. Subsequent to this flanking and backward imputation, if the HCV RNA value remains missing at a specific time point, then the subject will be considered as virological failure at this time point (i.e., not undetectable or unquantifiable).

If a subject starts another treatment for HCV, then all HCV RNA values for this subject measured on or after the start date of the new HCV treatment will be excluded from analyses. The subject will be considered a failure for summaries of viral response at all time points after the start of the new HCV treatment.

Due to the non-interventional nature of this study several different methods for determination of the HCV RNA value can be applied. For the purpose of the statistical analysis, a HCV RNA measurement is considered <50 IU/mL,

- if a PCR test was used

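### Read literally, the SAP's FACIT-Fatigue missing-item rule replaces a 0-52 summed total with a 0-4 item average; the prorating and norming formulas need to be written out.

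*SAP*

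**What the plan says.** The FACIT-Fatigue paragraph of SAP section 4.2.7.2.3 describes 13 items, each scored 0 to 4, and says that the scale "yields a summed total score ranging between 0 and 52". It adds that "FACIT-Fatigue will be normed to 0-100", without a formula, and that "Higher FACIT-Fatigue scores indicate a lesser degree of fatigue".

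For skipped items, provided that at least 7 of the 13 are answered, it says that "the total score will be imputed with the average score of the answered items in the same scale". What is imputed is the total score, not the missing items, and no multiplication by 13 follows.

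No other text supplies the missing step:

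- SAP section 4.2.3 only points back: "The discussion of missing data imputation for the PRO endpoints is included in section 4.2.7.2.3".
- The protocol describes the questionnaire (sections 9.4.1.6 and 9.7.5, Annex 1) but gives no scoring rule. Its section 9.7.1 allows imputation only for the HCV RNA endpoints.
- The SAP reference list has no FACIT scoring guide.
- The WPAI, in the same SAP section, does get explicit formulas and coding rules.

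**The concern.** The total and the value that replaces it are on different scales: one is a sum of 13 items, the other an average of single items. A programmer who follows the sentence would put a number between 0 and 4 into a variable that runs from 0 to 52 for everyone else.

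The harm would come from mixing the two. A patient with a complete form at baseline and one skipped item later would show a large false change, and the reverse pattern would show a false change in the other direction. The SAP plans descriptive statistics by visit, changes from baseline, and an ANCOVA with the baseline score as covariate. All three would take in these outliers, and a mis-scored baseline would also be an extreme covariate value. FACIT-Fatigue is collected at several visits and serves the secondary objective on patient-reported outcomes, so each patient has several chances to skip an item.

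**Working it through.** **Inputs** (SAP section 4.2.7.2.3): 13 items; item range 0-4; total is the sum; minimum 7 items answered. The SAP gives no norming formula; 100/52 is used below unless stated otherwise.

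**The plan's own figures.** Range: 13 x 0 = 0 to 13 x 4 = 52, as stated. Threshold: 7/13 = 53.8% and 6/13 = 46.2%, so the two phrasings of the 50% condition give the same cut of 7 items. Both figures reproduce.

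**Two readings for a form with k answered items (7 to 12) and sum S.**

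- Literal: total = S/k, which always lies between 0 and 4.
- Prorated: total = S x 13/k, the same as filling each skipped item with the patient's own mean and then summing.
- Ratio: (S/k) / (13 x S/k) = 1/13, whether one item or six are skipped.

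| Item mean | Literal total | Prorated total | Literal x 100/52 | Prorated x 100/52 | Difference, 0-100 |
|---|---|---|---|---|---|
| 1 | 1 | 13 | 1.9 | 25.0 | -23.1 |
| 2 | 2 | 26 | 3.8 | 50.0 | -46.2 |
| 3 | 3 | 39 | 5.8 | 75.0 | -69.2 |
| 4 | 4 | 52 | 7.7 | 100.0 | -92.3 |

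**One form.** Eight items at 3 and four at 2, one skipped: S = 32, k = 12, mean 2.67. Prorated: 32 x 13/12 = 34.7 (66.7 on 0-100). Literal: 2.67 (5.1 on 0-100).

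**One change score.** Item mean 3 at both visits, complete at baseline and one item skipped later: the prorated change is 39 - 39 = 0; the literal change is 3 - 39 = -36.

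**Effect on a visit mean (illustration).** The documents give no rate of incomplete forms and no expected score. Assume that true totals are normal with mean 39 and SD 10, with values outside 0-52 set to the limit, and that a fraction f of forms is incomplete at random. The shift is approximately -f x (39 - 3) = -36f.

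| f (assumed) | Fall in mean, 0-52 | SD (9.2 with no incomplete forms) |
|---|---|---|
| 2% | 0.7 | 10.4 |
| 5% | 1.8 | 11.8 |
| 10% | 3.6 | 13.8 |

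If out-of-range values are discarded and not set to the limit, the SD starts at 8.5 and rises to 9.7, 11.1 and 13.0. The pattern is the same.

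**The case against.** Several points on the other side have weight.

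- **The wording may be shorthand.** The paragraph calls the total a 0-52 sum, and a more-than-half condition usually goes with filling skipped items by the patient's own mean. Read that way, the rule is prorating and the score is right. This is plausible and cannot be ruled out, but the sentence does not say it.
- **The condition, taken literally, also covers complete forms.** At least 50% answered includes 13 of 13. If every form received the average, all scores would share a 0-4 scale and no contrast between complete and incomplete forms would arise. The distortion shown above therefore needs the rule to be applied to incomplete forms only. That is the natural sense of an imputation rule, but it is an assumption. A 0-4 score for everyone would still contradict the stated range.
- **Norming could hide the problem.** If the average is normed on its own range (100 x mean/4), item means of 1 to 4 give 25, 50, 75 and 100, identical to the normed prorated sum. This would need one norming formula for complete forms and another for incomplete ones, and the SAP states neither. It does not help un-normed scores, which SAP section 4.2.9 lists for interim analyses one to four.
- **Checks exist.** SAP section 5 requires program validation and plausibility checks, and tabulated minimums would show totals of 0 to 4. These checks could catch the error; they do not define the score.

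A reader might infer that patients who skip an item are in fact being scored as almost maximally fatigued. The documents do not support that. Neither the programs nor the table shells (SAP Part II) are supplied, so no mis-scored form is shown. The direction of the error also rests on the SAP's statement that high scores mean less fatigue. The SAP notes as reversed only items 7 and 8; if only those two are reversed and 0 means not at all, a patient without fatigue totals 11 x 0 + 2 x (4 - 4) = 0 and a maximally fatigued patient totals 11 x 4 + 2 x (4 - 0) = 52, the opposite direction. The factor of 13 does not depend on direction.

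**Conclusion.** The rule is wrong as written: it gives a 0-4 value for a score defined on 0-52, and nothing else in the protocol or SAP corrects it. If followed literally for incomplete forms only, each affected total is 1/13 of the prorated sum, an error of 36 points on 0-52 at an item mean of 3 (69.2 on 0-100 when normed by 100/52).

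The group-level figures are illustrations: they depend on the assumed share of incomplete forms and the assumed score distribution. Whether any score has been or will be computed this way is unknown. The consequence is limited to one secondary patient-reported outcome; SVR12 and the safety analyses do not use it. Two readings that differ 13-fold on incomplete forms still leave the score without a clear pre-specification, so the sentence should be corrected.

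**What to change.** Replace the imputation sentence in SAP section 4.2.7.2.3 with:

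> If at least 7 of 13 items are answered, total score = (sum of answered, direction-corrected items) x 13 / (number of answered items); otherwise missing. Normed score = total x 100/52.

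State in the same place which items are reversed, so that direction-corrected has one meaning and agrees with the stated direction of the score. Then check the existing scoring code and the FACIT-Fatigue outputs of the interim analyses against the formula; totals of 0 to 4 on incomplete forms would be the sign of a literal implementation.

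The cost is a short SAP edit, at most a line of code, and a check of outputs already produced. If the code already prorates, the change only documents it.

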#### **Assessment of work productivity and activity impairment – WPAI Hep C V2.0**

The WPAI questionnaire will be used to measure work absenteeism, work presenteeism, and daily activity impairment. The WPAI Hep C V2.0 is the HCV specific questionnaire that will be used in this study. Respondents are asked about time missed from work and time while at work during which productivity was impaired in the past seven days. Results of WPAI are expressed as a percentage of impairment from 0 to 100, with higher percentages indicating greater impairment and less productivity:

- % Presenteeism – percentage of impairment while working due to health problem
- % Absenteeism – percentage of work time missed due to health problem
- % Total work productivity impairment (TWP) – percentage of overall work impairment due to health problem
- % Total activity impairment (TAI) – percentage of general (non-work) activity impairment due to health problem

The WPAI Hep C v2.0 consists of 6 questions aimed at the following targets:

Q1.currently employed (yes, no)  
Q2.hours missed due to hepatitis C in the last seven days  
Q3.hours missed due to other reasons in the last seven days  
Q4.hours actually worked in the last seven days  
Q5.degree hepatitis C affected productivity while working  
Q6.degree hepatitis C affected regular activities

The four scores will be derived according to the WPAI-SHP scoring manual [4] as follows:

1. % absenteeism:  $100 \times Q2 / (Q2 + Q4)$
2. % presenteeism:  $100 \times Q5 / 10$
3. % TWP:  $100 \times \{Q2 / (Q2 + Q4) + [Q4 / (Q2 + Q4)] \times Q5 / 10\}$
4. % TAI:  $100 \times Q6 / 10$

The coding rules for contradictory or missing information are:

- If Q1 = YES or Q1 = NO or missing and hours missed or worked > 0, then employed. If Q1 = missing and hours missed and worked = 0, then not employed.
- If hours worked = 0, then productivity while at work is not applicable.
- A score will be set to missing if one or more of the items Q1-6 that are needed for the calculation of the score are missing. No imputation will be performed for missing items.
- Someone who missed all work hours due to health is 100% impaired.

The summary table will present the absolute and relative frequencies of employed and unemployed patients and descriptive statistics (n, mean, median, SD, minimum and maximum) for the four scores for baseline and the post-baseline time points by cirrhosis status and treatment regimen.

#### **4.2.7.2.4 Attitude towards self-management, medication and support**

The attitude towards self-management, medication and support will be analyzed for the CP.

##### **Patient Activation Measure – (PAM-13)**

The Patient Activation Measure (PAM) 13 is a measure used to assess the patient knowledge, skill, and confidence for self-management [5]. The PAM-13 item scale is a measure used to assess the patient knowledge, skill, and confidence for self-management. Each of the 13 items can be answered with one of four possible response options, which are “disagree strongly” (1), “disagree” (2), “agree” (3), “agree strongly” (4).

The scoring will be done by Insignia Health. If there are less than nine items answered, no summary score will be calculated.

A summary table will show descriptive statistics (n, mean, median, SD, minimum and maximum) of the score for baseline and the post-baseline time points, as well as changes from baseline, by cirrhosis status and treatment regimen. In addition, analysis of covariance (ANCOVA) will be applied to investigate the effect of the different ABBVIE REGIMENS ( $\pm$  RBV) by cirrhosis status on the score using the corresponding baseline value as covariate.

**Table 9** Overview of Outputs for Secondary Variables

Output Title	Output Short Name	Analysis Population
Liver Fibrosis Assessment Results by Genotype and Cirrhosis Status - CP - <country>	tlfa_<c>_gc_cp	Core population
Liver Fibrosis Assessment Results by Treatment Regimen and Cirrhosis Status - SP - <country>	tifa_<c>_tc_sp	Safety population
PRISM by Treatment Regimen and Cirrhosis Status - CP - <country>	tsis_<c>_tc_cp	Core population
FACIT-Fatigue by Treatment Regimen and Cirrhosis Status - CP - <country>	tfa_<c>_tc_cp	Core population
WPAI by Treatment Regimen and Cirrhosis Status - CP - <country>	twp_<c>_tc_cp	Core population
PAM-13 by Treatment Regimen and Cirrhosis Status - CP - <country>	tpam_<c>_tc_cp	Core population

The layouts of the tables mentioned above are provided in Part II of the SAP (Table Shells).

